2.5. Definition of Study Dates and Observation Period End Dates

The study dates and period end dates will be used to define the time period for data included in the analysis of efficacy and safety endpoints for the different observation periods (defined in Section 2.6).

Study Day 1 date: the date of randomization of the subject.

End-of-Study (EOS): the date of the last study-related procedure for the subject (EOS is defined as last assessment day during the study, including the Day 210/Post-Treatment Follow Up visit) and is defined as the minimum (last assessment day during the study, death date).

Double-Blind period start date will be the date of randomization.

Double-Blind period end date will be defined as the completion/early withdrawal date (date of completion or early withdrawal [any reason including death] from the double-blind period).

Up-to-Day 180 observation period end date will be defined as follows;

- Day 180/EODB completion date (for subjects who completed the double-blind period) or
- Death date (subjects who died during the double-blind period [DB reason=death] or during any time from randomization through Day 180 [died post withdrawal from DB but before Day 180/EODB visit] or
- Maximum (double-blind withdrawal date, randomization date + 180 days) for subjects who withdrew early from the double-blind period [any reason other than death] and had not died during the time from randomization through Day 180

First dose date: the date on which the first dose of study drug is taken by the subject. If missing or partial for a subject who takes study drug, the first dose date is set to the randomization date.

Last dose date: the date on which the last dose of study drug is taken by the subject (dose end date). If the dose end date is missing or partial for a subject who takes study drug, the last dose date is set as follows

- Maximum (Minimum (discontinuation date in the double-blind period [including death date during double-blind period], last visit date when drug is dispensed + number of pills dispensed - number of pills returned at following visit), imputed partial last dose date, exposure start date of last record))
 - Imputation rule for partial dates: If only the day is missing, then day imputed to the last day of that month. If day and month are missing, the date will be imputed to the start date if year is the same, else imputed to January 1st.

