2.6.2. On-Treatment Observation Period

This observation period includes data from the day of the **first dose of study drug to 2 days after the last dose of the study drug, inclusively** (dose dates defined in Section 2.5).

All randomized subjects will be included in the On-Treatment observation period. A conservative approach will be used for subjects who were randomized but never dosed to include any event that may occur even if the subject did not take study drug. This is defined to include VTE-related events that occur during the study even if the subject had not taken study drug. Only those events that occur prior to the double-blind period end date will be included in the on-treatment observation period.

Event: All efficacy and safety events (with respect to deaths, *VTE-related deaths are counted as events for primary efficacy composite endpoint. For Bleeding related deaths, major bleeding is counted as events for the primary safety endpoint*) that occurred from the date of first dose of study drug up to the last dose of study drug+2 days will be included in the analysis of the On-Treatment observation period.

- Event time - The time to event is defined as the time from first dose date to the time of the first event during this observation period.
 - For randomized subjects but never dosed: The time to event will be defined as the time from randomization to the time of the event during the time in study. This imputation rule will be applied only for the ITT population.

Censoring: Subjects who do not experience an event during this observation period will be censored.

Subjects who died during this observation period will be censored as of their death date for endpoint analysis not related to death.

- Censoring time - The time to censoring is defined as the time from first dose date to the minimum (earliest) of (last dose date+2 days, death date).
 - For randomized subjects but never dosed the time to censoring will be defined as the time from randomization to the minimum of (last day of their complete assessment for study outcomes during the double-blind period [double-blind completion/withdrawal], death date [non VTE-related deaths for primary efficacy composite endpoint]).

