4.4. Extent of Exposure

Duration of double-blind treatment is defined as the duration between the first dose date and last dose date, inclusive. Duration of treatment exposure will be summarized by treatment group.

Total treatment duration = last dose date - first dose date + 1.

The total number of temporary drug interruptions (>3 days) and reasons for interruptions will also be summarized by treatment group.

Duration of double-blind period will also be summarized. The duration of double-blind period is defined as the duration from randomization up to the double-blind period end date.

Duration of Double-Blind period = Double-blind period end date (completers or withdrew subjects) – randomization date + 1.

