6.1.2.1. Definition

The primary safety endpoint is defined as the time from the first study drug to first occurrence of ISTH major bleeding events in Section 6.1.1 during the ‘**On-Treatment**’ observation period (observation periods defined in Section 2.6).

Censoring - subjects who do not experience endpoint events during the ‘**On-Treatment**’ observation period will be censored at the minimum of (last dose date + 2, death date).

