6.2. Adverse Events

The original terms used in the CRFs by investigators to identify AE will be coded using the Medical Dictionary for Regulatory Activities (MedDRA) version 20.0 or higher.

A treatment-emergent adverse event (TEAE) is defined as any adverse event that starts between the first study medication administration and the last study medication administration + 2 days.

Only the AEs with start dates between the first dose date and the last dose date+2 days will be included in all TEAE summaries, including study (double-blind period) withdrawal and treatment discontinuation.

As per the protocol (Section 12.4), in this study suspected outcome events are excluded from AE/SAE collection and reporting, regardless of seriousness or severity. These suspected events will be captured on the eCRF as outcome events and will be waived from SAE collection and unblinding and exempted from expedited reporting. These events include: symptomatic lower extremity proximal DVT, asymptomatic lower extremity proximal DVT, symptomatic lower extremity distal DVT, symptomatic upper extremity DVT, symptomatic non-fatal PE, incidental PE, VTE-related death, all-cause mortality, ATE events (e.g., MI, stroke), visceral VTE, and all bleeding events.

The number (%) of subjects who had treatment-emergent adverse events will be summarized by System Organ Class (SOC) and preferred term (PT) for the Safety analysis population.

The number and percentage of subjects experiencing TEAEs will be summarized by treatment group for the Safety analysis population, and stratification factor: APC or non-APC.

In addition, overall summaries of **all AEs** (all AEs that are reported from start of study through the Day 210/End-of-Study) for the safety population will also be presented. Summary table of AE by body system and preferred term will also be presented for all AEs.

Adverse events will also be summarized by treatment group, severity, relationship to study medication, combined severity and relationship to study medication, action taken during treatment, and subject outcome. They will also be presented by treatment group, SOC, and PT.

Differences in the percentages of AEs between the two groups will be summarized and the 95% CI for the difference using the normal approximation to binomial distribution will be provided.

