6.2.1. Imputation Rules for Missing AE Dates

A conservative approach will be used to handle the missing dates for adverse events. The rules for handling the incomplete AE onset dates will be as follows:

- If only the day is missing, and the month and year are known, the month and year of the AE will be compared with the month and year of double-blind medication start date.
 - If the both the month and year of the AE is equal to the month and year of double-blind medication start date, then the imputed day will be the start day of medication.
 - If the month or the year of the AE are different, then the imputed day will be the 1st day of the month.
- If only the month is missing, and day and year are known, the year of the AE will be compared with the year of the double-blind medication start date.
 - If the year of the AE is equal to the year of the double-blind medication start date, then the imputed month will be the same as the month of the double-blind medication.
 - If the year is different, then the month will be as January.
- If both the day and month are missing but year is known, compare the year with the year of the double-blind medication start date.
 - If the year is the same, then impute the AE start date as the same as the first dose date.
 - If the year is different, then impute the AE start date to be January 1.
- If the day, month and year are all missing, then the imputed date for the AE will be the date of the first dose of study medication.

After imputation if the AE start date is greater than the AE end date, then the AE start date will be set equal to the AE end date.

- No imputation will be done for AE end date.

6.2.2. Adverse Events Resulting in Withdrawal from the Study and Discontinuation of Treatment:

The number and percentage of subjects who withdrew from the double-blind period due to an **TEAE** (TEAE led to withdrawal from the study) will be summarized by treatment group and listed by subject. In addition, **TEAEs** that led to discontinuation of study drug (drug withdrawal) will also be summarized by treatment group.

In addition, overall summaries of **all AEs** (all AEs that are reported from start of study through the Day 210/End-of-Study) with action taken of drug withdrawal will also be presented

6.2.3. **Serious Adverse Events (SAE) and Deaths during the Study:**

The number and percentage of serious TEAE and deaths will be summarized by treatment group and listed by subject.

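### A partial first dose date is set to the randomization date even when its recorded month or year is later, so some certainly drug-free days count as on-treatment time

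*SAP*

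**What the plan says.** Section 2.5 of the SAP treats a wholly missing and a partial first dose date alike: "If missing or partial for a subject who takes study drug, the first dose date is set to the randomization date". It sets no condition on a known month or year, and no other section limits the rule.

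The resulting date is the starting point for much of the safety analysis:

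- On-Treatment period (2.6.2): "The time to event is defined as the time from first dose date to the time of the first event during this observation period". Censoring times have the same origin.
- Primary safety endpoint (6.1.2.1): "The primary safety endpoint is defined as the time from the first study drug to first occurrence of ISTH major bleeding events". The secondary bleeding endpoints (6.1.4.2) follow the same approach.
- Treatment-emergent adverse events (6.2): "Only the AEs with start dates between the first dose date and the last dose date+2 days will be included in all TEAE summaries".
- Exposure (4.4): "Total treatment duration = last dose date - first dose date + 1". Compliance (4.3) also uses this date.
- The Post-First Dose period (2.6.4), used for a supportive efficacy analysis.

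Elsewhere the SAP keeps a known month. For a partial last dose date, in the same Section 2.5: "If only the day is missing, then day imputed to the last day of that month". For a partial adverse event onset outside the medication start month (6.2.1): "If the month or the year of the AE are different, then the imputed day will be the 1st day of the month". Bleeding start dates (6.1.1) follow the same pattern, and a partial efficacy event date (5.1.2) goes to the first of its known month.

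**The concern.** An imputation rule should fill in what is unknown and leave alone what is known. If the day of the first dose is missing but the month is recorded and is later than the month of randomization, the randomization date is not a possible first dose date. The rule assigns it anyway.

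The interval between randomization and the start of the recorded month then enters the analysis as time on drug. A major bleed or adverse event in that interval is classed as on-treatment although no drug had been taken. Event and censoring times measured from first dose become too long by the same interval. At stake is the correct classification of events and time in the bleeding, treatment-emergent and exposure summaries, and in the supportive On-Treatment and Post-First Dose efficacy analyses.

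**Working it through.** The SAP states no figure that depends on this rule, so there is none to reproduce. The check is date arithmetic on assumed dates.

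**Definitions.** R = randomization date; M1 and M2 = first and last day of the recorded first-dose month, with M1 after R. Under Section 2.5 the imputed start is R. The true start lies between M1 and M2.

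- Certain drug-free days counted as on-treatment = M1 − R
- Largest possible number = M2 − R
- Part that the recorded month lets one remove = M1 − R
- Part that remains unknown = 0 to M2 − M1

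**Example 1.** R = 28 March, first dose in April, day unknown.

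- Certain: 1 April − 28 March = 4 days
- Largest possible: 30 April − 28 March = 33 days
- Removable: 4 days. Remaining uncertainty: 33 − 4 = 29, so 0 to 29 days

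**Range.** With first dose in April and R anywhere in March:

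| R | Certain excess (days) | Largest possible (days) |
|---|---|---|
| 1 March | 31 | 60 |
| 15 March | 17 | 46 |
| 28 March | 4 | 33 |
| 31 March | 1 | 30 |

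**Exposure.** R = 15 March, last dose 30 June, duration as in Section 4.4.

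- SAP rule (start 15 March): 108 days
- Start 1 April: 91 days, so 108 − 91 = 17 days are certainly wrong
- Start 30 April: 62 days, so at most 108 − 62 = 46 days are wrong

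**Compliance.** Both formulas in Section 4.3 have the form 1 − i/D, where D is the denominator and i the days in D not on drug. Adding g days to numerator and denominator gives 1 − i/(D + g), a rise of i·g / [D(D + g)]. With D = 91 and g = 17 this is 17/(91 × 108) = 0.0017, about 0.17 percentage points per day not on drug, and zero if there are none. The effect is minor.

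**Second partial date in the same subject** (Example 1 dates):

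| Partial bleed or AE date | SAP start 28 March | Start 1 April |
|---|---|---|
| March, day unknown | months match, so moved to 28 March: on-treatment at time zero | months differ, so 1 March: before start, excluded |
| April, day unknown | months differ, so 1 April: on-treatment | months match, so 1 April: on-treatment |

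Only the event in the randomization month changes. It certainly preceded an April first dose, yet the present rule counts it as on-treatment.

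**Same-month case.** If the recorded month is the month of randomization, the randomization date is the earliest compatible date and does not conflict with the record.

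**The case against.** The strongest reply is that the case may never arise. Section 1.5 has drug dispensed on Day 1, which Section 2.5 defines as the randomization date. The conflict needs both an unknown day and a first dose in a later calendar month. The SAP gives no count of such subjects. This stands, and it limits the importance of the point.

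A second reply is that an early start is conservative, because it widens the window in which bleeds and adverse events are captured. That is fair when the whole date is missing or the known month is the randomization month. It does not justify overriding a recorded later month: events before any drug cannot be caused by it, and including them would tend to pull a comparison of the arms towards no difference.

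A third reply is that the SAP uses anchor dates elsewhere, for example for adverse events known only by a year equal to that of first dose (6.2.1). Different rules for different variables are indeed not a contradiction. The fault lies in what this rule does to recorded data, not in its differing from the others.

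A reader might go further and infer that all 33 days in Example 1 are a correctable error, that partial bleeding and adverse event dates in general inherit a wrong start, that compliance is materially distorted, or that the bleeding hazard ratio is biased to a known extent. The SAP supports none of these. Only 4 of the 33 days are provably wrong, the inherited error needs a second partial date falling in the randomization month, the compliance effect is minor, and no effect on a hazard ratio can be derived.

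**Conclusion.** The point holds, as a minor one. For a partial first dose date whose recorded month or year is later than that of randomization, Section 2.5 assigns a date the record excludes. The provable error per affected subject is the interval from randomization to the start of the recorded month (or year): 4 days for 28 March and April, 1 to 31 days over all March randomization dates. It always runs towards too early a start.

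It reaches the primary and secondary bleeding endpoints, treatment-emergent summaries, exposure, and the supportive On-Treatment and Post-First Dose efficacy analyses. The primary, key secondary and additional secondary efficacy analyses run from randomization (2.6.1, 5.2.2, 5.4.2, 5.6.2) and are untouched. The summaries of all adverse events from the start of the study do not depend on the first dose date.

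The example dates are assumptions. The number of affected subjects is unknown and probably small.

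**What to change.** Replace the first-dose imputation sentence in Section 2.5 with a rule of this kind: for a partial first dose date in a subject who took study drug, use the later of the randomization date and the earliest date compatible with the recorded parts, that is, the 1st of the recorded month, or 1 January of the recorded year if only the year is known. When the date is wholly missing, use the randomization date as now.

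No separate cap is needed, because Section 2.5 already keeps the last dose date from preceding the first. The cost is one sentence and one line of derivation code, with no new data. Results for subjects with complete first dose dates do not change. It would also help to report how many first dose dates were imputed, and how many of those had a recorded month or year later than that of randomization.

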The last dose date will not be later than the double-blind period end date. The last dose date will not be before the first dose date and if a subject has not taken any study drug, the last study drug date will be set to missing.

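### When only the day of the last dose is missing, the SAP sets the date to month-end regardless of the pill count, which can add up to 30 off-drug days to the On-Treatment window

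*SAP*

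**What the plan says.** SAP Section 2.5 gives one formula for a last dose date that is missing or partial. It begins "Maximum (Minimum (discontinuation date in the double-blind period [including death date during double-blind period], last visit date when drug is dispensed" and, after adding the pills dispensed at that visit, ends "number of pills returned at following visit), imputed partial last dose date, exposure start date of last record". The discontinuation date and the pill-count date sit inside a minimum. The imputed partial date and the start of the last exposure record sit beside that minimum, in the outer maximum.

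Two imputation rules feed the partial-date term:
- Day missing, month known: "If only the day is missing, then day imputed to the last day of that month".
- Day and month missing: "the date will be imputed to the start date if year is the same, else imputed to January 1st".

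One upper limit follows: "The last dose date will not be later than the double-blind period end date". That date is defined by completion or withdrawal, not by stopping drug: "Double-Blind period end date will be defined as the completion/early withdrawal date". Sections 1.2.1 and 4.6 say that permanently stopping study drug does not in itself take a subject out of the double-blind period.

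The last dose date then closes several windows. In the primary safety analysis (Section 6.1.2.1), a subject without an event "will be censored at the minimum of (last dose date + 2, death date"). The same two-day tail defines the On-Treatment period (Section 2.6.2), the secondary bleeding analyses (6.1.4.2), the TEAE window (6.2) and the On-Treatment efficacy analyses (5.2.3). The last dose date also sets treatment duration (4.4).

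**The concern.** Knowing the month should narrow the last dose date. Here it pushes the date to the latest day that the month allows. If the end date is wholly missing, the partial-date term drops out and the pill-count/discontinuation minimum normally decides. If only the year is known, the imputed date is early and the same minimum normally stands. Only when the month is known as well is that evidence set aside. The rule is therefore inconsistent with itself, and the SAP gives no reason for choosing month-end.

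The subjects exposed to this are those who stop drug and remain in follow-up. Their off-drug days, and any bleeds or adverse events on those days, would be classed as on treatment. Extra unexposed time can pull a bleeding hazard ratio toward 1, and events more than two days after the last dose can be counted as treatment-emergent.

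**Working it through.** The SAP states no figure on this point, so there is nothing to reproduce. The check is to apply the rule literally to example dates.

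**Formula (Section 2.5).** Let D = discontinuation date, P = pill-count date, I = imputed partial date, S = start of last exposure record, F = first dose date and E = double-blind end date.

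Last dose = max{ F, min[ E, max( min(D, P), I, S ) ] }

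**Bracket check.** As printed, the formula opens two brackets and closes three. The reading above is the natural one. If every term were placed inside the minimum, the maximum would have a single argument and the result could never be later than the start of the last record, which makes no sense as a last dose date.

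**Example dates (assumptions, not trial data).** Randomization and first dose are on 10 January 2017, so randomization + 180 days is 9 July 2017. The recorded last dose has month and year only. D is read as the drug-stop date in the first two cases.

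| Case | True last dose | D | P | E | I | Result | Excess (days) |
|---|---|---|---|---|---|---|---|
| Stops drug, stays to Day 180 | 10 Mar | 10 Mar | 8 Mar | 9 Jul | 31 Mar | 31 Mar | 21 |
| Stops drug on the 1st, stays | 1 Mar | 1 Mar | 1 Mar | 9 Jul | 31 Mar | 31 Mar | 30 |
| Withdraws from double-blind | 10 Mar | 12 Mar | 8 Mar | 12 Mar | 31 Mar | 12 Mar (cap) | 2 |
| Dies | 10 Mar | 10 Mar | 8 Mar | 10 Mar | 31 Mar | 10 Mar (cap) | 0 |
| Completes | 8 Jul | 9 Jul | 8 Jul | 9 Jul | 31 Jul | 9 Jul (cap) | 1 |

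In the first row, min(10 Mar, 8 Mar) = 8 Mar and max(8 Mar, 31 Mar) = 31 Mar. The cap of 9 July does not bind. The On-Treatment window closes on 2 April instead of 12 March.

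**Does the meaning of D matter?** Suppose D is instead the double-blind end date, 9 July in the first row. Then min(9 Jul, 8 Mar) = 8 Mar and the maximum is again 31 Mar. The excess is still 21 days. What changes is which evidence is displaced: only the pill count, not a recorded drug-stop date.

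**Year-only date.** For the subject in the first row, I becomes the start date, 10 January. The maximum returns 8 Mar, so nothing is overridden.

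**Average excess where the cap does not bind.** If the true day is uniform over a 365-day year, the excess in a month of n days sums to n(n − 1)/2:
- seven 31-day months: 7 × 465 = 3,255
- four 30-day months: 4 × 435 = 1,740
- February: 378

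Total 5,373; 5,373 / 365 = 14.7 days, range 0 to 30.

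**The case against.** The best defence is that a late end date is a reasonable choice for a safety window. It captures more bleeds and adverse events, and the SAP leans to inclusive handling elsewhere, for example for never-dosed subjects in Section 2.6.2. A pill count can also fall too early when doses are missed, and Sections 4.3 and 4.4 expect interruptions. The maximum keeps the result from falling before the recorded month unless the cap applies. This much stands: a later date is not always wrong, and any replacement must respect the recorded month. It does not explain why a known month should discard evidence that a missing month would keep.

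Several stronger readings are tempting but unsupported:
- **That the rule overrides the discontinuation date in general.** Section 2.5 does not say whether this means stopping drug or leaving the double-blind period. On the second meaning it coincides with the cap and is never overridden.
- **That every partial date moves by about two weeks.** The mean of 14.7 days applies only where the cap does not bind. In the examples, a death, a withdrawal and a completer gain 0, 2 and 1 days.
- **That the pill-count term is a day late.** This holds only if the first pill from the last bottle is taken on the dispensing day, which the SAP does not state.
- **That partial dates are known to occur.** The amendment history for v6.0 says that an imputation rule was added. It reports no such dates.
- **That the comparison of arms is biased by a known amount.** The same rule applies to both arms, and the documents give no basis for an estimate. The primary efficacy analysis uses the Up-to-Day 180 period and does not depend on the last dose date.

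**Conclusion.** The point holds for a specific group: subjects with only the day of the last dose missing who stopped drug and stayed in the double-blind period. For them Section 2.5 sets the last dose to month-end unless the double-blind period ends first. This displaces an earlier pill-count date in that month, and an earlier drug-stop date if that is the date intended. The addition is 0 to 30 days per affected subject, about 14.7 on average under a uniform true day with no cap binding.

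The conclusion rests on the natural reading of a formula whose brackets do not balance. How many subjects are affected cannot be worked out from the SAP, so the overall effect is probably small. It is a minor correction, worth making because it touches the primary safety window and the rule contradicts its own handling of less complete dates.

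**What to change.** 1. State which discontinuation date Section 2.5 means, and balance the brackets.
2. When month and year are known, use the month as bounds. Start from the minimum of the drug-discontinuation date and the pill-count date, leaving the pill-count term as it is. Raise it, if necessary, to the later of the first day of the recorded month and the start of the last exposure record. Then limit it to the earliest of the last day of that month, the drug-discontinuation date and the double-blind end date. Omit the drug-discontinuation date where none exists. Query any record in which these bounds conflict.

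On the example dates, the two subjects who stop drug and stay would get 8 March and 1 March, so the excess of 21 and 30 days becomes −2 and 0. The −2 simply reflects a pill count assumed to be two days early.

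That is the cost in accuracy: missed doses can make the result somewhat early, and the first-of-month floor limits this. If the recorded month were March and the pill count pointed to 20 February, the floor would give 1 March or later. If the sponsor prefers to err late, keeping month-end but bounding it by the drug-discontinuation date gives 10 March and 1 March in the same two cases, with no excess.

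The change is confined to one derivation and needs no new data. Reporting the number of imputed last dose dates by arm would show whether it mattered.
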